1.5.3 Rationale for ATLCAR.CD30 in Pediatric Subjects with CD30+ Lymphoma

HL occurs in both children and adults; the American Cancer Society projects that 8,500 new cases of HL will be diagnosed in the US in 2016 (3,710 in females and 4,790 in males). HL is a common malignancy in young adults [47] (ages 15 to 40),

peaking incidence persons 20s in in in their [http://www.cancer.org/cancer/hodgkindisease/detailedguide/hodgkin-diseasekey-statistics]. Although rare in children less than 5 years of age, approximately 10-15% of HL cases are diagnosed in children and teenagers. The long term impact of therapy for HL on quality of life is of special concern given that this disease often impacts a much younger cohort of subjects than the typical malignancy. Thus, treatment of HL requires a careful balance between providing effective therapy to cure the disease while minimizing the toxic effect of therapy that could result in excessive long-term treatment-related complications [47].

Although approximately 90% of limited stage HL subjects are projected to be cured with standard of care therapy (i.e., multi-agent chemotherapy \pm radiation), many do not live their expected life span due to delayed treatment-related toxicities that include secondary malignancies and cardiovascular disease [48, 49]. For example, the preferred treatment option for early stage I or II non-bulky HL with favorable prognosis is the use of chemotherapy (e.g., doxorubicin, bleomycin, vinblastine, and dacarbazine; ABVD) with or without involved-field radiation therapy [50-52]. In a recent retrospective study, survivors of HL treated with chemotherapy alone had a lower incidence of secondary malignancies with a 30-year cumulative incidence of 5.8%, compared to 24.7% in HL subjects who received consolidative radiation [53]. Given the unclear overall survival advantage, and the long-term toxicities associated with consolidative radiation, the use of this modality remains controversial in the treatment of HL. In addition, both an increased dose of radiation and anthracycline exposure were associated with significantly increased risk of cardiovascular complications [54]. While the use of interim PET/CT to guide treatment of limited stage disease can identify subjects who need less intensive therapy, treatment for those with high-risk disease is more intensive and acute, and long-term complications of therapy remain a concern. Furthermore, salvage chemotherapy for subjects who relapse includes high-dose chemotherapy followed by a stem cell transplant [52]. While effective, the intensity of this approach also leads to long-term treatment-related comorbidities such as secondary acute myeloid leukemia and myelodysplastic syndrome [55, 56]. Although the two leading causes of death in HL survivors are second malignancies and cardiovascular disease, other key late complications include atherosclerotic disease, pulmonary disease, and endocrine dysfunction such as hypothyroidism and infertility [57].

In addition to the risks associated with therapies for HL, current thinking is that the success of traditional chemotherapy and radiation-based strategies for the treatment of pediatric malignancies has reached a plateau, especially in subjects with relapsing or refractory disease [58]. The additive toxicities and limited efficacy of conventional regimens in achieving a cure has led to Phase I studies in pediatric cancers of immune-based or molecularly targeted therapies to prevent relapse or treat minimal disease.

As noted in section 1.5.2, of the over 250 trials incorporating CAR-T cells registered on the https://clinicaltrials.gov/ website, there are currently at least 30 studies that have allowed for pediatric enrollment with the majority of these trials being conducted in CD19+ hematologic malignancies [36, 58]; moreover, these approaches are showing promise. For example, a CD19-directed CAR therapy study conducted at the Children's Hospital of Philadelphia reported outcomes in 25 children with ALL, the majority of whom had received prior SCT [31]. Complete remissions were achieved in up to 90% of these subjects, which included 2 children previously treated with blinatumomab. In addition, event-free and overall survival at 6 months in these subjects were 67% and 78%, respectively and durable remissions of up to 24 months have been observed. Other CD19 CARs studies enrolling pediatric subjects are also reporting promising outcomes in ALL with manageable toxicity [28, 59]. Moreover, CARs are in development targeting other lymphoid and myeloid antigens such as CD13, CD20, CD30 and CD33 [58]. Clinical trials targeting these antigens are currently ongoing, with promising preliminary data reported for ATLCAR.CD30 therapy in relapsed/refractory CD30+ lymphomas as discussed in the next section.

As noted in section 1.4 above, the CD30 antigen is expressed on almost all HLs at diagnosis and at relapse; and its viability as a target has been confirmed with the success of brentuximab vedotin [4], an antibody-drug conjugate that targets CD30. Brentuximab vedotin produces objective tumor responses in HL, albeit with limited durability and serious toxicities reported in 31% of subjects. The hope is that CD30-directed CAR-T therapy, which appears safe thus far (see section 1.5.5), will provide durable responses and improve outcomes in adult and pediatric subjects with HL and other CD30+ lymphomas. Moreover, ALTCAR.CD30 therapy should reduce the risks of long-term complications that are associated with available therapies for HL, which is a special concern for pediatric subjects.

1.5.4 ATLCAR.CD30

After constructing a CAR targeting CD30 [60, 61], Drs. [name] and [name] demonstrated in preclinical studies that T-lymphocytes engineered to express this receptor are redirected to kill CD30+ HL cell lines [42, 62].

The success rate for manufacturing of cells is 100%. At Baylor College of Medicine, cell lines have been manufactured for 18 subjects starting from a median of 2.4×10^7 PBMCs (range 3.6×10^6 to 4.9×10^7). During cell manufacture, 3 subjects became ineligible due to rapid worsening of their performance status and 1 subject was not infused because his tumor was subsequently shown to be CD30-negative. One subject was still in remission and without evidence of disease post SCT and 1 subject went on to another phase I study. At the time of protocol submission, 3 subjects were awaiting assessment of eligibility for ATLCAR.CD30 treatment. We

therefore consider the number of subjects accrued but unable to receive ATLCAR.CD30 cells as limited. Subjects who did not receive treatment were ineligible to receive cells post SCT for clinical or other reasons. No subjects were unable to receive ATLCAR.CD30 treatment due to issues related to manufacturing failure.

1.5.5 Phase I Trial of ATLCAR.CD30 for Relapsed/Refractory CD30+ Lymphoma

At Baylor Drs. [name] and [name] recently completed dose escalation in a phase I trial designed to determine if ATLCAR.CD30 was safe for therapy of CD30+ HL and CD30+ NHL and would persist in these subjects long enough to potentially control disease.

ATLCAR.CD30 were given to 9 subjects (7 with HL and 2 with CD30 + ALCL) with relapsed/refractory HL or CD30+ NHL. Eight of the 9 subjects had relapsed or progressed after treatment with brentuximab vedotin. Two were treated on dose level (DL) 1 (2×10^7 CAR-T/m²), two on DL2 (1×10^8) and five on DL3 (2×10^8), without any conditioning regimen before T cell infusion, as mandated by FDA to exclude occurrence of "on target-off tumor" toxicities. CAR-T cell infusions produced no attributable adverse events, and none of the subjects developed a CRS. Nine subjects were evaluable for antitumor responses. At 6 weeks after treatment, 4 subjects had stable disease, 1 had PR and 1 had a CR, while 3 subjects (1 of whom with ALCL) had disease progression [63].

After establishing the safety and persistence of ATLCAR.CD30 in the nontransplant setting, LCCC1524-ATL is designed to determine if these cells are safe for consolidation therapy following autologous transplant and will persist in subjects with CD30+ HL or NHL long enough to potentially control or prevent disease after high dose therapy and ASCT.

1.6 Study Design and Rationale

ASCT may be the only curative option for subjects with refractory/relapsed hematological malignancies. Despite ASCT, disease recurrence remains the major cause of treatment failure. Hence development of non-toxic consolidation treatments after transplant remains a highly desirable objective, and the adoptive transfer of CTLs is one promising approach [64-67].

In this Phase I multicenter study, peripheral blood will be collected for production of ATLCAR.CD30 cells in subjects with CD30⁺ lymphoma at high risk of relapse post-transplant, and scheduled to undergo ASCT. Three dose levels will be evaluated to identify the MTD in this population: Level $1 = 2 \times 10^7 \text{ CAR}^+ \text{ T cells/m}^2$; Level $2 = 1 \times 10^8/\text{m}^2$; Level $3 = 2 \times 10^8/\text{m}^2$. The total number of cells infused will be calculated on the number of CAR-T cells as requested by the FDA. Similar to the prior phase I

LCCC1524-ATL
Administration of T lymphocytes Expressing the CD30 Chimeric Antigen Receptor (CAR)
for Prevention of Relapse of CD30+ Lymphomas after High Dose Therapy and Autologous
Stem Transplantation (ATLAS)
ATLCAR.CD30

summarized in section 1.5.5, we will monitor the persistence of these infused cells in the peripheral blood of the subjects and whenever lymph nodes are biopsied as per routine clinical care during the first year after treatment at the tumor site by measuring the level of the transgene by both phenotypic and molecular analyses. Currently, we can regularly detect a single transduced cell in 50,000 peripheral blood mononuclear cells by real-time PCR amplification. Moreover, because gene persistence and expression may not correlate with antitumor effector function, we will also determine the functionality of the peripheral blood T cells *ex vivo*.

Ex vivo expanded, polyclonally activated T cells have been infused as early as two days after stem cell transplant in myeloma subjects without significant side effects [68]. However, since the study we propose will be the "first in man" application of ATLCAR.CD30⁺ T cells after ASCT, we will infuse these cells after ASCT once hematologic recovery is evident (see section 4.1.2 for this definition). By using this conservative approach, we believe we will be able to infuse T cells in an environment in which homeostatic mechanisms favor lymphoid expansion [69] without interfering with stem cell engraftment. It is now evident that non-myeloablative conditioning is required to allow high level expansion of CAR-T cells and obtain optimal anti-tumor efficacy [70, 71]. ASCT creates a lymphodepleted environment, with production of high levels of homeostatic cytokines such as IL-7 and IL-15 that induce expansion of the infused CAR-T cells in the absence of competing endogenous lymphoid cells for the homeostatic cytokines [69].

The ability to combine CAR-based therapies with ASCT will reduce tumor immune evasion of this cell therapy. Tumor cells use several mechanisms to evade immune responses, by generating hostile chemokine and cytokine milieus or by recruiting inhibitory cells such as Tregs and Th2 cells. This may limit the benefits of CAR-based therapies [72]. ASCT depletes Tregs and disrupts the tumor microenvironment improving the prospects for CAR⁺T cell persistence, expansion and anti-tumor activity. HL and ALCL in particular will provide a useful model for studying this postulate since HL and ALCL cells release inhibitory molecules and ligands (TGF β , IL-10, Fas-L) and attract suppressive T-cell subsets including Th2 and Tregs [73, 74].

As outlined above, toxicities and even deaths [45, 69] due to "tumor lysis syndrome" and "cytokine storms" have occurred in subjects with high tumor burden when they received CAR-T cells. This is likely the result of rapid and massive T-cell activation through their CAR/costimulatory molecule complex followed by the release of cytokines (IFN γ , TNF α , IL-6 etc.). These potentially lethal toxicities should be limited if CAR-T cells are infused after ASCT, since the burden of targeted tumor will be minimized. [44, 45]. We will collect serum before and after infusion for cytokine monitoring, and continue to monitor subjects for 4 hours after infusion.

2.0 STUDY OBJECTIVES

- 2.1 Primary Objective
- 2.1.1 To determine the safety and tolerability and to estimate the MTD of ATLCAR.CD30 post ASCT in subjects with CD30+ lymphoma at high risk for relapse.
- 2.2 Secondary
- 2.2.1 To measure the survival of ATLCAR.CD30 in vivo
- 2.2.2 To estimate PFS after infusion of ATLCAR.CD30 post ASCT in subjects with CD30+ lymphoma at high risk for relapse
- 2.2.3 To determine the overall survival after infusion of ATLCAR.CD30 post ASCT in subjects with CD30+ lymphoma at high risk for relapse
- 2.3 Exploratory
- 2.3.1

3.0 STUDY ENDPOINTS

3.1 Primary

3.1.1 Toxicity will be classified and graded according to the National Cancer Institute's Common Terminology Criteria for Adverse Events (CTCAE, version 4.0) and CRS toxicity will be graded according to the toxicity scale outlined in 18.8 (APPENDIX VII- CRS Toxicity Grading Scale and Management Guidelines). The MTD will be based on the rate of dose-limiting toxicity (DLT; see Sections 4.1.3.2 and 4.1.3.3).

3.2 Secondary

- 3.2.1 PFS is defined from day of ASCT to relapse (in subjects with a documented complete response after ASCT) or progression (in subjects with documented stable disease or partial response after ASCT), or death as a result of any cause as per the Revised Response Criteria for Malignant Lymphoma (see APPENDIX II-Revised Response Criteria for Lymphoma) [74].
- 3.2.2 Overall survival will be measured from the date of administration of CAR.CD30 transduced ATL to date of death.
- 3.2.3 Persistence of CAR.CD30 T cells in vivo will be determined by quantitative PCR and flow cytometry in peripheral blood samples.

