3.3 Exploratory

This study is a multicenter, open-label phase I clinical trial testing the hypothesis that the administration of ATLCAR.CD30 to subjects with CD30+ lymphoma post autologous transplant is safe as evidenced by the rate of DLT. The rate of DLT will be used to determine the MTD; see section 4.1.3.2. Three dose levels of ATLCAR.CD30 will be evaluated to determine a recommended dose in adult and pediatric subjects. Initially, only adults will be enrolled during the dose escalation phase of the study. Once a dose level has been tested in at least 2 adults without the occurrence of DLTs during the assessment period, children may then be enrolled on that dose level according to the CRM. Each subject will receive one injection followed by close monitoring over the subsequent 6 weeks. See section 7.4 for schedule of longer term follow-up.

Subjects scheduled to undergo an ASCT at one of the protocol sites for treatment of lymphoma will be approached for consent to screening and potential enrollment into LCCC1524-ATL. Peripheral blood cells will be collected from consenting subjects who meet eligibility for cell procurement for creation of ATLCAR.CD30 cells (see section 4.1.1) prior to ASCT. The ASCT, including mobilization and collection of PBSCs, administration of myeloablative therapy, reinfusion of PBSCs and supportive care following transplant will be as per routine standard of care, and not expected to be impacted by enrollment into LCCC1524-ATL. Post ASCT, subjects who meet eligibility criteria for treatment will receive one infusion of ATLCAR.CD30 cells once there is evidence of hematologic recovery as defined in section 4.1.2. Research personnel will keep track of any subjects who undergo procurement but do not undergo treatment with ATLCAR.CD30 cells, and the reason for withholding treatment.

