 - 15. ATLCAR.CD30 cells infused after evidence of hematologic recovery post ASCT, see section 4.1.2 for definition of recovery. This will generally occur between 14 and 20 days following infusion of autologous stem cells following high-dose chemotherapy. All subjects will receive their ATLCAR.CD30 infusion at the lead site, the University of North Carolina, Chapel Hill.
 - 16. Patient reported outcomes (PRO) will be measured by the PROMIS Global Health and Physical Function questionnaires and selected items from the NCI PRO-CTCAE (see section 7.6 and APPENDIX V - Patient Reported Outcomes Surveys) (optional). PRO questionnaires will only be offered to adult study participants. PRO questionnaires will first be given at time of screening consent. On the day of infusion, subjects will fill out questionnaires prior to infusion. These questionnaires are optional and may not be given to all subjects.
 - 17. Long Term Follow Up: If a subject develops a delayed adverse event that is related to the trial drug, then more frequent (2-4 times per year) clinical observation may be indicated. Appropriate follow up will be conducted based on a particular subject's prior test results. The investigator will determine the additional testing and sample collection that is needed. New malignancies and delayed adverse events will be recorded during long term follow-up.

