11.3 Data Analysis Plans

11.3.1 Safety Analysis of Adverse Event Data

All subjects who received the ATLCAR.CD30 infusion will be included in the safety analysis. Adverse event data and corresponding toxicity grades six weeks after T-cell infusion and during long-term follow-up will be summarized in the form of tables. Incidence tables will be generated to summarize incidence of subjects reporting at least one episode of each specific adverse event, incidence of adverse events causing withdrawal and incidence of serious adverse events. The total number of episodes for each event reported (Frequency Table), the severity and attribution to study therapy of each episode reported (Severity Table and Attribution Table) will also be displayed.

Listings of adverse events by subjects will include the time to onset, the duration of each event, the severity of each event, and the relationship of the event to study therapy, whether it was a serious event, and whether it caused withdrawal. Safety data will be summarized for the overall subject group and by dose levels.

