11.3.4 Analysis of Progression Free Survival

PFS is defined in section 3.2.1. We will estimate PFS using the Kaplan-Meier method.

Page 101 of 154

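### PFS is timed from ASCT although its objective asks for PFS after infusion; in infused subjects this gives a small upward bias

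*Combined protocol and SAP*

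**What the plan says.** Two secondary objectives in section 2.2 have the same form. Objective 2.2.2 reads "To estimate PFS after infusion of ATLCAR.CD30 post ASCT in subjects with CD30+ lymphoma at high risk for relapse" and objective 2.2.3 reads "To determine the overall survival after infusion of ATLCAR.CD30 post ASCT in subjects with CD30+ lymphoma at high risk for relapse".

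The endpoints in section 3.2 do not follow them in the same way. For OS, 3.2.2 says "Overall survival will be measured from the date of administration of CAR.CD30 transduced ATL to date of death". For PFS, 3.2.1 says "PFS is defined from day of ASCT to relapse (in subjects with a documented complete response after ASCT) or progression", and the Study Summary repeats this. No reason is given for the different origin.

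On the gap between the two dates, footnote 15 of the Time & Events Table (and sections 4.1.2 and 7.2.3) says of the infusion: "This will generally occur between 14 and 20 days following infusion of autologous stem cells following high-dose chemotherapy". No upper limit is stated.

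The whole analysis plan for PFS in 11.3.4 is a reference to 3.2.1 and the sentence "We will estimate PFS using the Kaplan-Meier method". It names no population, delayed entry or landmark. For safety, by contrast, 11.3.1 is explicit: "All subjects who received the ATLCAR.CD30 infusion will be included in the safety analysis". The study plan (section 4.0) also foresees subjects who never reach infusion: "Research personnel will keep track of any subjects who undergo procurement but do not undergo treatment with ATLCAR.CD30 cells".

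**The concern.** A subject reaches infusion only by surviving the transplant, recovering hematologically and meeting the pre-infusion criteria. If PFS is estimated in infused subjects but the clock starts at ASCT, no one in the analysis can have died between ASCT and infusion. Progression in that interval is also unlikely to be recorded: the baseline scan precedes ASCT, and the next protocol scan is 6 to 8 weeks after infusion (section 7.8). A plain Kaplan-Meier estimate treats these subjects as at risk throughout an interval that they had to survive to be included. This is guaranteed (immortal) time, and it pushes the curve up.

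At stake is whether the reported PFS answers objective 2.2.2. PFS and OS would also start about half a month apart, although their objectives are worded alike. PFS is secondary and purely descriptive: no test, threshold or dose decision uses it.

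**Working it through.** The plan gives no expected PFS, event count or precision target, so there is no figure of its own to reproduce. The check sizes the shift.

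**Inputs**
- Lag from ASCT to infusion: 14 to 20 days (section 4.1.2; footnote 15 of the Time & Events Table).
- Sample size: 12 to 18 (section 11.2).
- Reference medians: 24.1 and 42.9 months, the placebo and active arms of the post-ASCT consolidation trial described in section 1.4. They are used for scale only; the documents do not state that trial's PFS origin.
- Assumptions: exponential PFS from infusion, infused subjects only, no event recorded before infusion.

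**Shift in the median.** 14/30.44 = 0.46 months and 20/30.44 = 0.66 months. Every infused subject's time lengthens by the lag, so the median rises by the same amount. Any progression recorded before infusion would reduce this, so it is an upper figure for that lag.

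**Shift at 12 months.** With S(t) = exp(−ln 2 × t / median) from infusion and lag d, the ASCT-origin curve is S(t − d). So S(12) is compared with S(11.54) and S(11.34).

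| Assumed median | From infusion, S(12) | From ASCT, 14-day lag | From ASCT, 20-day lag | Difference (points) |
|---|---|---|---|---|
| 24.1 months | 0.708 | 0.718 | 0.722 | +0.94 to +1.35 |
| 42.9 months | 0.824 | 0.830 | 0.833 | +0.61 to +0.88 |

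A simulation of 2,000,000 subjects (median 24.1 months, lag uniform on 14 to 20 days, infused subjects only) agrees: 12-month PFS is 71.9% from ASCT against 70.8% from infusion, and the median is 24.6 against 24.1 months.

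**Scale against sampling error.** SE = √(S(1 − S)/n), ignoring censoring.
- S = 0.708: 10.7 points at n = 18 and 13.1 at n = 12.
- S = 0.824: 9.0 points at n = 18 and 11.0 at n = 12.
- Smallest ratio: 0.61/11.0 = 0.06. Largest: 1.35/10.7 = 0.13.
- The Study Summary gives 40 subjects. At n = 40 the SE for S = 0.708 is 7.2 points and the largest ratio is 1.35/7.2 = 0.19.

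**Scale against the assessment schedule.** Scans at 6, 12, 18 and 24 months carry a window of ±1 month (footnote 9 of the Time & Events Table). The 14 to 20 day shift is smaller than that.

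**Sensitivity to the lag.** The 14 to 20 days are what generally happens, not a bound. An assumed lag of 42 to 60 days with a 24.1-month median would add 2.9 to 4.1 points at 12 months.

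**The case against.** **ASCT is a reasonable origin.** The product is studied as consolidation after transplant. The only protocol baseline scan precedes ASCT, so an ASCT clock starts closer to a disease measurement than an infusion clock does. The wording of objective 2.2.2 could describe the treated setting rather than time zero. This has some force, and rewording 2.2.2 would cure the mismatch in words. It would not remove the guaranteed time: an ASCT-origin curve in infused subjects still needs delayed entry. The parallel OS objective, which is timed from infusion, also favours the plainer reading.

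**The bias is conditional.** This stands. It requires an infused-only analysis set, which 2.2.2 implies but 11.3.4 does not state. Analysing all transplanted subjects from ASCT would leave no guaranteed time, but the result would include subjects who were never infused and would not be PFS after infusion.

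**The interval is not strictly event-free.** A reader might infer that it is. The documents do not support that. Infusion guarantees survival, but the criteria in 5.2 and 5.3 do not exclude relapse after ASCT. History and physical examination, with a dermatology consult for cutaneous lymphoma, are listed before infusion (7.2.2) and could detect it.

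**The effect is trivial and the amendment late.** The effect is small, which is why the point is minor. Dated versions run from April 2016 to April 2023, so PFS outcomes may already exist, though the documents do not say. That argues for a dated amendment and for keeping the ASCT-origin curve visible, not for leaving the estimate as it is.

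**Conclusion.** The point holds and is minor. As written, PFS is not timed as objective 2.2.2 asks. If infused subjects are analysed, plain Kaplan-Meier from ASCT overstates PFS slightly: by up to 0.46 to 0.66 months on the median for a 14 to 20 day lag, and by about 0.6 to 1.4 points at 12 months. At the planned 12 to 18 subjects this is 0.06 to 0.13 of a standard error. The 12-month figures rest on assumed exponential PFS, medians borrowed from another trial, and no event recorded before infusion. The direction does not depend on the borrowed medians. The primary DLT/MTD result is unaffected.

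Two stronger readings are tempting but not supported. One is that the PFS and OS curves cannot be compared at all; the offset is about half a month and both dates are known, so they can be read together with care. The other is that the parenthetical references in 3.2.1 to a documented response after ASCT drop progression found at the first post-ASCT assessment. They more naturally say which term applies to which subject. Footnote 9 provides for documented progression at the 6-week scan, and Appendix II defines progressive disease without requiring an earlier post-ASCT response.

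**What to change.** In 11.3.4, name infused subjects as the PFS analysis set and estimate PFS for objective 2.2.2 from the date of infusion. Amend 3.2.1 and the Study Summary to match.

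State how progression found between ASCT and infusion is handled. Such a subject has the event before the infusion clock starts, and under delayed entry would never join the risk set, so the rule and the number of such subjects should both be reported.

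If the ASCT-origin definition in 3.2.1 is kept, report that curve alongside, with left truncation (delayed entry) at infusion. Date the amendment, because the documents do not say whether PFS outcomes have already accrued.

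Cost: reported PFS times become about half a month shorter and a secondary endpoint definition changes. No extra scans or subjects are needed.
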